5.1 Treatment groups

The arms included in efficacy tables are based on the treatment sequence (picturing also the up-titration) for the periods up to the final lock at week 260. Two separate columns will display the assigned and actual treatment resulting in the following treatment sequences:

Efficacy:

- AIN457 10 mg/kg - 75 mg
- AIN457 10 mg/kg - 75 mg - 150 mg
- AIN457 10 mg/kg - 75 mg - 300 mg
- AIN457 10 mg/kg - 150 mg
- Placebo - AIN457 75 mg
- Placebo - AIN457 75 mg - 150 mg
- Placebo - AIN457 75 mg - 300 mg
- Placebo - AIN457 150 mg

After week 52 the combination of assigned treatment will also be shown.

- AIN457 75 mg & Placebo - AIN457 75 mg
- AIN457 150 mg & Placebo - AIN457 150 mg

The treatment sequence following up-titration for the combined groups will be:

- AIN457 75 mg & Placebo - AIN457 75 mg - 150 mg
- AIN457 75 mg & Placebo - AIN457 75 mg - 300 mg
- AIN457 150 mg & Placebo - AIN457 150 mg – 300 mg

Cases might up-titrate twice; for these cases the treatment prior to each up-titration will be displayed (that is not the assigned treatment for the 2nd observed up-titration). Therefore, at the graphical representation of up-titration the actual treatment dose prior to the switch will be displayed.

Regarding safety, the arms included in the entire treatment period are as follows.

- Any AIN457 75 mg
- Any AIN457 150 mg
- Any AIN457 300 mg
- Any AIN457 (if appropriate)

Placebo group will be included at the in-text tables and listings of the CSR.

In the safety listings the groups will be the following:

- AIN457 10 mg/kg - 75 mg
- AIN457 10 mg/kg - 150 mg
- Placebo AIN457 75 mg
- Placebo AIN457 150 mg
- Placebo not re-randomized.

6 Subgroup definitions

The primary endpoint and secondary endpoints will be evaluated for TNF-alpha inhibitor status and by concomitant MTX use (ACR20/50, [REDACTED]).

7 Assessment windows, baseline and post baseline definitions, missing data handling

Baseline and post-baseline definitions

In general, a *baseline* value refers to the core study and is the last measurement made prior to administration of the first dose of study treatment in core. Baseline information will be presented appropriately in the “by visit” summaries in both safety and efficacy tables.

A post-baseline value refers to a measurement taken after the first dose of study treatment in core study.

Analysis visit windows

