13.1 Pharmacokinetics

All completed subjects with quantifiable pharmacokinetic (PK) measurements of secukinumab will be included in the pharmacokinetic data analysis. Serum concentrations will be expressed in mass per volume units. All concentrations below the limit of quantification as well as missing data will be labeled as such in the concentration data listings. PK concentrations will be summarized by visit and treatment group. In addition to mean, standard deviation (SD), coefficient of variation (CV), median and quartiles, the geometric mean and geometric coefficient of variation (CV) and n(log) will be presented. The formula for deriving the geometric mean and CV (%) is as following:

- $CV (\%) = (SD/mean) * 100$,
- $geometric\ mean = \exp(\text{sum of log transformed data} / \text{number of non-missing data points after log transformation})$,
- $geometric\ CV = \sqrt{\exp(\text{variance of log-transformed data}) - 1} * 100$.

In addition, sample number, concentration, sample date, sample time at pre-dose and minutes pre-dose will be listed by treatment sequence.

Values below lower limit of quantification/below detection limit will be imputed by 0.

Pharmacokinetic data of the study treatment will be analyzed with a population-pharmacokinetic mixed effects model. The analysis will be based on a pooled data set, including pharmacokinetic samples from previous studies. The modeling approach will be further detailed in a modeling plan. Results will be reported separately.

14 Safety evaluation

Safety analyses will be done on the safety set.

Summaries will be presented cumulatively from core and extension. For subjects who switched from placebo to secukinumab in core, their data prior to switch will only be reported in in-text tables and listings.

Safety analyses will be performed on treatment received or actual treatment as described below:

The actual treatment or treatment received for summaries of safety data will differ to the treatment assigned at randomization if a subject received the wrong treatment during the core and extension study or if the subject up-titrated to a higher dose.

Subjects who switch treatment during the study (e.g. from placebo to active treatment, or had dose escalation) will be counted to both groups using the appropriate start and stop exposure date.

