gamma-glutamyl transferase (GGT), alanine aminotransferase (ALT), aspartate aminotransferase (AST), alkaline phosphatase (ALP), glucose, cholesterol, triglycerides (TG).

These summaries will be split into hematology and chemistry for study level reports and the pooled summary of clinical safety.

Shift tables will be presented comparing baseline laboratory result (CTCAE grade) with the worst results (expressed in CTCAE grade) during the treatment phase (either initial or entire) analyzed. Of note, baseline will be defined as last assessment prior to first dosing in the initial treatment phase of the core study. Subjects with abnormal laboratory values will be listed and values outside the normal ranges will be flagged.

Table 14-2 CTCAE grades for laboratory parameters to be analyzed

CTCAE v4.0 Term	Grade 1	Grade 2	Grade 3	Grade 4
HGB decreased (Anemia)	<LLN – 100 g/L	<100 – 80 g/L	<80 g/L	Life-threatening consequences; urgent intervention indicated
Platelet count decreased	<LLN – 75.0 x10e9 /L	<75.0 - 50.0 x10e9 /L	<50.0 – 25.0 x10e9 /L	<25.0 x 10e9 /L
White blood cell decreased	<LLN - 3.0 x 10e9 /L	<3.0 - 2.0 x 10e9 /L	<2.0 - 1.0 x 10e9 /L	<1.0 x 10e9 /L
Neutrophil count decreased	<LLN - 1.5 x 10e9 /L	<1.5 - 1.0 x 10e9 /L	<1.0 - 0.5 x 10e9 /L	<0.5 x 10e9 /L
Lymphocyte count decreased	<LLN - 0.8 x 10e9/L	<0.8 - 0.5 x 10e9 /L	<0.5 - 0.2 x 10e9 /L	<0.2 x 10e9 /L
Creatinine increased*	>1 - 1.5 x baseline; >ULN - 1.5 x ULN	>1.5 - 3.0 x baseline; >1.5 - 3.0 x ULN	>3.0 baseline; >3.0 - 6.0 x ULN	>6.0 x ULN
TBL increased	>ULN - 1.5 x ULN	>1.5 - 3.0 x ULN	>3.0 - 10.0 x ULN	>10.0 x ULN
GGT increased	>ULN - 2.5 x ULN	>2.5 - 5.0 x ULN	>5.0 - 20.0 x ULN	>20.0 x ULN
ALT increased	>ULN - 3.0 x ULN	>3.0 - 5.0 x ULN	>5.0 - 20.0 x ULN	>20.0 x ULN
AST increased	>ULN - 3.0 x ULN	>3.0 - 5.0 x ULN	>5.0 - 20.0 x ULN	>20.0 x ULN
ALP increased	>ULN - 2.5 x ULN	>2.5 - 5.0 x ULN	>5.0 - 20.0 x ULN	>20.0 x ULN
Glucose increased (Hyperglycemia)	>ULN - 8.9 mmol/L	>8.9 - 13.9 mmol/L	>13.9 - 27.8 mmol/L	>27.8 mmol/L
Glucose decreased (Hypoglycemia)	<LLN - 3.0 mmol/L	<3.0 - 2.2 mmol/L	<2.2 - 1.7 mmol/L	<1.7 mmol/L
Cholesterol high	>ULN - 7.75 mmol/L	>7.75 - 10.34 mmol/L	>10.34 - 12.92 mmol/L	>12.92 mmol/L
Hypertriglyceridemia	1.71 - 3.42 mmol/L	>3.42 - 5.7mmol/L	>5.7 - 11.4 mmol/L	>11.4 mmol/L

*Note: for “creatinine increased” the baseline criteria do not apply

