Summaries for newly occurring or worsening clinically notable lipid abnormalities will also be provided cumulatively for each of the following parameters and categories:

- HDL:
 - ≤LLN
 - <0.8 x LLN
- LDL, cholesterol, triglycerides:
 - ≥ULN
 - >1.5 x ULN
 - >2.5 x ULN

Newly occurring or worsening liver enzyme abnormalities will also be summarized based on the event criteria given in [Table 14-3](#):

Table 14-3 Liver-related events

Parameter	Criterion
ALT	>3xULN; >5xULN; >8xULN; >10xULN, >20xULN
AST	>3xULN; >5xULN; >8xULN >10xULN; >20xULN
ALT or AST	>3xULN; >5xULN; >8xULN >10xULN; >20xULN
TBL	>1.5xULN, >2xULN, >3xULN,
ALP	>2xULN, >3xULN. >5xULN
ALT or AST & TBL	ALT or AST >3xULN & TBL >2xULN; ALT or AST >5xULN & TBL >2xULN; ALT or AST >8xULN & TBL >2xULN; ALT or AST >10xULN & TBL >2xULN
ALP & TBL	ALP >3xULN & TBL >2xULN ALP >5xULN & TBL >2xULN
ALT or AST & TBL & ALP	ALT or AST >3xULN & TBL >2xULN & ALP <2xULN (Hy's Law) Note: elevated ALP may suggest obstruction as a consequence of gall bladder or bile duct disease; ALP may also be increased in malignancy. FDA therefore terms Hy's Law cases as indicators of pure hepatocellular injury . This does not mean that cases of ALT or AST >3xULN & TBL >2xULN & ALP ≥2xULN may not result in severe DILI.

Notes: 1) In studies which enroll subjects with pre-existing liver disease, baseline LFT may be increased above ULN; in such a case it is meaningful to add the condition “and worse than baseline” to the abnormality criteria

For a combined criterion to be fulfilled, all conditions have to be fulfilled on the same visit. The criteria are not mutually exclusive, e.g. a subject with ALT = 6.42xULN is counted for ALT >3xULN and ALT >5x ULN.

Individual subject laboratory data listings will be provided for all subjects as well as for subjects with newly occurring or worsening CTCAE grades, or with newly occurring or worsening after baseline abnormalities in lipid parameters, or with newly occurring or worsening after baseline abnormalities in liver enzymes.

No box plots over time or other graphs will be presented for any of the laboratory parameters.

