No visit windows were used in case of up-titrations. The before up-titration measurement is considered as the last visit measurement, performed on or before the date that patient took the up-titration dose. The up-titration data analysis will be based on week intervals; it is accounting for the time period between the actual date of exposure to the up-titrated dose and the last visit date of the subject:

- 4 – 8 weeks after up-titration
- 12 – 32 weeks after up-titration
- 36 – 56 weeks after up-titration
- 60 – 80 weeks after up-titration
- 84 – 104 weeks after up-titration

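### With a single core baseline, lab abnormalities carried over from a lower dose count as new on the higher dose, and those carried over from core placebo count as new on secukinumab

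*SAP*

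**What the plan says.** **Baseline.** SAP Section 7 sets one general rule: the baseline "value refers to the core study and is the last measurement made prior to administration of the first dose of study treatment in core". Section 14.2 repeats it for the CTCAE shift tables: "baseline will be defined as last assessment prior to first dosing in the initial treatment phase of the core study".

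**New or worsening abnormalities.** For lipids, Section 14.2 says: "Summaries for newly occurring or worsening clinically notable lipid abnormalities will also be provided cumulatively". For liver tests it says: "Newly occurring or worsening liver enzyme abnormalities will also be summarized based on the event criteria". Neither sentence names a reference value. The matching listings are of subjects with "newly occurring or worsening after baseline abnormalities in liver enzymes", which leads back to the Section 7 baseline. Section 14.3 adds newly occurring notable vital signs and uses the core baseline for change.

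**Columns.** SAP Section 5.1 defines the safety columns as Any 75 mg, Any 150 mg, Any 300 mg and, if appropriate, Any AIN457. Lab summaries are by dose. Under Section 14, a subject who switches from placebo or escalates "will be counted to both groups using the appropriate start and stop exposure date".

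**Window.** Lab data are on-treatment from the first secukinumab dose in core to 84 days after the last dose (Section 14.2).

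**A pre-escalation reference exists, but only for efficacy.** Section 12.4 starts the ACR shift tables from the visit before up-titration, and Section 17.1 defines that value: "The before up-titration measurement is considered as the last visit measurement", taken on or before the date of the up-titration dose.

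**The concern.** Whether a lab value is new depends on what it is compared with. Escalation is possible only from Week 156 (Protocol Sections 3.1 and 5.5.5), so for an escalated dose the core baseline is at least three years old and precedes all lower-dose exposure. An abnormality that began on 75 mg can then appear as an abnormality of 300 mg.

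Protocol Section 5.5.5 forbids dose reduction after escalation, so the carry-over runs only from lower to higher dose. The core arms were 75 mg and 150 mg (Protocol Appendix 11), so Any 300 mg consists of escalators, with no subjects treated at that dose from the start to dilute the effect.

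Placebo switchers raise a related problem. Their baseline precedes placebo, but their lab window opens at first secukinumab. An abnormality that arose on placebo and persists falls inside the window and is new relative to baseline. Treatment-emergent AEs are instead referenced to first secukinumab (SAP Section 14.1).

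At stake is the secondary safety objective as displayed by dose: the summary tables would not tell onset on a dose from persistence.

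**Working it through.** The documents give no abnormality rate, persistence rate or number escalated, so there is no stated figure to reproduce. The check has two parts.

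**1. One subject traced through the rules.** Assumed ALT: 0.8×ULN at core baseline, 3.5×ULN on 75 mg, 3.4×ULN after escalation to 300 mg. The criteria are >3×ULN (SAP Table 14-3) and CTCAE grade 2, >3.0 to 5.0×ULN (SAP Table 14-2).

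| Reference for the 300 mg column | Any 75 mg | Any 300 mg | Worst shift shown on 300 mg |
|---|---|---|---|
| Core baseline (SAP) | counted | counted again | normal to grade 2 |
| Last value before escalation | counted | not counted | grade 2 to grade 2 |

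The value fell slightly on 300 mg, yet under the SAP rule it is a new event on 300 mg. Any AIN457 counts the subject once either way.

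**2. Illustrative size among escalators.** Let
- q = share first abnormal on the lower dose;
- s = share of those still or again abnormal on the higher dose;
- r = share truly new on the higher dose, among those not abnormal before.

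Core reference: q×s + (1−q)×r. Reference that removes carry-over: (1−q)×r. Difference: q×s.

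With r = 5% (all inputs assumed):

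| q | Core ref., s = 25% | s = 50% | s = 100% | Carry-over removed |
|---|---|---|---|---|
| 2% | 5.40% | 5.90% | 6.90% | 4.90% |
| 5% | 6.00% | 7.25% | 9.75% | 4.75% |
| 10% | 7.00% | 9.50% | 14.50% | 4.50% |
| 20% | 9.00% | 14.00% | 24.00% | 4.00% |

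The smallest excess is 0.02 × 0.25 = 0.5 percentage points and the largest is 0.20 × 1.00 = 20. The ratio of the two displays runs from 5.40/4.90 = 1.10 to 24.00/4.00 = 6.00.

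Three limits apply. The excess q×s does not depend on r. A carrier who worsens further on the higher dose counts under either reference, so q×s is an upper figure where s includes such subjects. An abnormality that was absent at the last pre-escalation visit and then recurs is removed only by using the worst lower-dose grade, not the last value.

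In Any 300 mg the excess applies to the whole column. In Any 150 mg it is multiplied by the share of that column who escalated, which the documents do not give.

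**Placebo switchers.** SAP Section 16 expects 140 to 160 of 460 to 520 extension subjects to come from placebo: 140/460 = 30.4% and 160/520 = 30.8%. This is a planning figure for those exposed to the misattribution, not a count of affected subjects.

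**The case against.** **The baseline sentence in Section 14.2 governs only the CTCAE shift tables.** This is correct. Those tables cross baseline grade with worst grade and label nothing as new. For the lipid and liver summaries the core reference follows from the general rule in Section 7 and the after-baseline wording of the listings. The SAP does not say outright that carried-over abnormalities are recounted. That is the result of applying its rules together. Programming specifications could add a carry-over rule, but the SAP has none.

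**The start and stop exposure date rule could be read as placing labs by onset.** A reader might also infer that AEs are explicitly protected from the same problem. The treatment-emergent definition in Section 14.1 refers to first secukinumab, not to the escalation date, so AE placement by dose rests on the same Section 14 sentence. But an AE has a recorded start date, whereas a lab value is new only by comparison with a reference, and the only one given is the core baseline. The firm contrast with AEs therefore concerns placebo switchers.

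**Placebo-onset abnormalities are not double counted in the main tables.** A reader might infer that they are. SAP Section 4 keeps core placebo safety data out of the post-text tables. What remains is misattribution to secukinumab, which also reaches Any AIN457.

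**Some abnormalities will not carry over.** Protocol Section 3.6 describes most grade 3 neutropenia as transient and reversible, and Protocol Section 5.5.9 requires discontinuation for clinically significant abnormalities judged to put the subject at risk. Both points favour lower values of q×s for those parameters. They say little about mild, persistent lipid or enzyme elevations.

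**Persistence can be traced elsewhere.** By-visit values, by-visit shifts and individual listings are planned. This stands, but it does not correct the summary percentages by dose.

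**A pre-escalation reference is already drug-exposed and would mix two baselines in Any 150 mg.** This is a real trade-off. Showing both versions answers it.

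**Conclusion.** The point holds. Under the stated rules, a lab abnormality that first appears on a lower dose and is present at a measurement after escalation meets the new-or-worsening definition in both dose columns, and the worst-grade shifts share the same core reference. An abnormality that arose on core placebo and persists is counted as a secukinumab abnormality. The direction is upward, mainly in Any 300 mg and in the escalated part of Any 150 mg.

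The size is not known. The range of 0.5 to 20 percentage points among escalators rests wholly on assumed q and s. A reader might infer that higher-dose rates are inflated several-fold. The documents do not support that: such ratios need a high q, near-complete persistence and a low true onset rate, none of which they give.

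Abnormalities that resolve before escalation and do not recur are not recounted. The tables are descriptive, the ACR results are unaffected, and Any AIN457 is affected only through placebo carry-over. An extension to ECG is weakly grounded, because Section 14.4 relies mostly on absolute thresholds and does not use the newly occurring label.

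**What to change.** Amend SAP Section 14.2, and Section 14.3 for newly occurring notable vital signs:

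1. **Escalated subjects.** In the higher-dose column, judge new-or-worsening abnormalities and worst shifts against the last value on or before the first dose at that level, as Section 17.1 already does for up-titration. Alternatively use the worst lower-dose grade, which also avoids recounting intermittent abnormalities. State which is chosen.
2. **Placebo switchers.** Use the last value before first secukinumab in all columns, including Any AIN457.
3. **Companion display.** Keep the core-baseline version alongside, and footnote which reference applies to each table.

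No new data are needed. Haematology and chemistry are scheduled at the on-site visits where escalation may be decided (Protocol Section 5.5.5 and Tables 6-1 to 6-3), and blood is drawn before dosing (Protocol Section 6.5). Lipids are drawn less often (Weeks 156, 180, 208, 232 and 260), so the pre-escalation lipid value may be some weeks old.

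The cost is a second baseline flag, two reference points within Any 150 mg, and a reference for escalators that already reflects exposure to secukinumab.

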Each new injection should be given at least one inch from the previously used site. If subject chooses the abdomen, 2 inches area around navel should be avoided. Investigational treatment should not be injected into areas where the skin is tender, bruised, red, or hard, or where the subject has scars or stretch marks. Injection sites should be rotated to reduce the risk of reaction.

Single syringes will be packed in individual boxes. The boxes containing the PFS with study treatment solution should be kept at 2 to 8°C (36°F to 46°F, do not freeze) and protected from light. Prior to administration, the unopened boxes containing the PFS should be allowed to come to room temperature in a place protected from light for approximately 20 minutes. Used

syringes should be disposed immediately after use in a sharps container OR according to the regulatory requirements in the respective country.

The caregiver or site staff will administer the injection only to those subjects who are not able to self-administer the PFS injection.

Domiciliary administration

Starting with week 132 (after initial 24 weeks of extension study of self-administered treatment under the supervision of site staff), subjects will be allowed to self-administer the PFS at home when they are not visiting the site for any other trial related procedures. The trial related safety and efficacy procedures will be conducted every 12-16 weeks during Treatment Periods 3, 4 and 5.

The subjects will be allowed to self-administer treatment at home (starting from Week 132) only if they have exhibited correct use for self-administering the PFS at the site during the first 24 weeks of treatment. At such time points, if requested by subjects, a caregiver would also be allowed to administer study medication after having received proper training by site staff and having exhibited ability to perform the injection procedure to the subject at the site.

It should be recorded on the corresponding eCRF(s) whether the subject self-administered the PFS and whether it was administered at home or at the site.

Prior to self-administration at home, subjects should contact the investigator / site staff in case they are experiencing any AE/SAEs or have any concerns.

If the subject is not able / not confident to self-administer the PFS, and the caregiver is unable/unwilling to perform the injection, he/she should visit the site every 4 weeks during the treatment period and site staff will administer the PFS.

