5.5.12 Early study termination

The study can be terminated at any time for any reason by Novartis. Should this be necessary, the subject should be seen as soon as possible and treated as a prematurely withdrawn subject. The investigator may be informed of additional procedures to be followed in order to ensure that adequate consideration is given to the protection of the subject's interests. The investigator will be responsible for informing IRBs and/or ECs of the early termination of the trial.

6 Visit schedule and assessments

Table 6-1, Table 6-2 and Table 6-3 list all of the assessments and indicate with an "X" when the visits are performed.

Subjects should be seen for all visits on the designated day or as close to it as possible. Subjects should not receive study medication within less than 2 weeks after the previous administration.

During the treatment periods, subjects may be seen at an unscheduled visit, e.g. if they experience deterioration of their condition, or AEs that in the opinion of the investigator need intervention or repeated laboratory testing. During these unscheduled visits, study treatment will not be administered. Subjects who discontinue study treatment will continue to be followed for safety assessments. They are not considered withdrawn from the study.

Subjects who discontinue study treatment before completing the study, and those who prematurely withdraw from the study for any reason should be scheduled for a study visit 4 weeks after their last study treatment administration, at which time all the assessments listed for EoT for the given treatment period (Week 156 or 208 or 260) will be performed (see [Section 5.5.9](#)). Subjects will then return to the study site 12 weeks after the last study treatment administration for further assessments as indicated under the follow-up visits (F268).

If they refuse to return for these assessments or are unable to do so, every effort should be made to contact them or a knowledgeable informant by telephone or by sending appropriate correspondence (i.e. certified letter) immediately. At this contact, the safety (e.g., potential occurrence of AE or SAE) and the primary reason for a subject's premature withdrawal should be determined.

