6.5.4 Laboratory evaluations

A central laboratory will be used for analysis of all specimens collected listed below (except urinalysis, UPT and ESR). Details on the collection, shipment of samples and reporting of results by the central laboratory are provided in the laboratory manual. For the identification of clinically notable values, see [Appendix 1](#). All subjects with laboratory tests containing clinically significant abnormal values are to be followed until the values return to normal ranges or until a valid reason, other than treatment related AE, is defined.

[REDACTED]

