6.5.4.2 Clinical chemistry

Serum chemistries will include glucose, urea, creatinine, total bilirubin, AST (SGOT), ALT (SGPT), GGT, alkaline phosphatase, sodium, potassium, bicarbonate, calcium, phosphorous, total protein, albumin, and uric acid.

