7.3 Liver safety monitoring

There has been no safety signal for liver toxicity with secukinumab to date in over 6000 patients exposed and from a mechanism of action standpoint there is no effect of blocking IL-17A on the liver. Liver function tests will be obtained at regular intervals but special measures for liver safety monitoring are not planned.

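### The same-visit rule keeps sequential ALT/AST and bilirubin rises out of the combined liver rows, and the SAP does not say whether unscheduled repeats count after Week 104

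*SAP*

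**What the plan says.** SAP Section 14.2 summarises liver abnormalities by the criteria in Table 14-3. There are separate rows for ALT, AST, ALT or AST, TBL and ALP, and combined rows for ALT or AST with TBL, for ALP with TBL, and for Hy's Law (ALT or AST above 3xULN, TBL above 2xULN, ALP below 2xULN). The rule for the combined rows is: "For a combined criterion to be fulfilled, all conditions have to be fulfilled on the same visit". No window in days across visits is given.

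Four other provisions bear on it:

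- **Schedule.** Protocol 5.5.4 says: "The trial related safety and efficacy procedures will be conducted every 12-16 weeks during Treatment Periods 3, 4 and 5".
- **Repeats.** Protocol Section 6 allows unscheduled visits, among other reasons for "AEs that in the opinion of the investigator need intervention or repeated laboratory testing". Protocol 6.5.4 adds: "All subjects with laboratory tests containing clinically significant abnormal values are to be followed until the values return to normal ranges", or until another valid explanation is found. Protocol 7.3 says "special measures for liver safety monitoring are not planned", so no retest timing is fixed.
- **Visit assignment.** Up to Week 104, SAP 17.1 maps unscheduled and repeat samples into analysis windows, and Table 17-2 takes the most extreme value in the window for notable abnormalities. After Week 104, SAP Sections 7 and 17.1 use the recorded nominal visit.
- **Coverage.** Under SAP Section 14 the safety summaries are cumulative over core and extension. Under 14.2 they include only laboratory data up to 84 days after the last dose.

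**The concern.** A follow-up sample after a raised transaminase will usually be drawn at a different visit from the sample that prompted it. If TBL crosses its limit only on that follow-up, when ALT/AST has already fallen below 3xULN, no single visit meets the combined criterion and the subject is not counted.

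The Hy's Law row is the one readers look to for liver safety, and it deals in counts so small that one subject matters. A zero would be read as no subject having had both abnormalities, when it means that no subject had them on one visit. No planned output pairs the values across visits.

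**Working it through.** **1. Reproduce the schedule.** Chemistry is marked in Protocol Tables 6-1 to 6-3 at Weeks 116, 128, 140, 156, 168, 180, 192, 208, 220, 232, 244, 260 and F268, following Week 104 of the core study. The gaps are 12, 12, 12, 16, 12, 12, 12, 16, 12, 12, 12 and 16 weeks, then 8 weeks to F268. This reproduces the stated 12-16 weeks on treatment. The visible core rows of the SAP 17.1 window table (Group 2) have targets at Weeks 60, 68, 76, 84, 92 and 104, so gaps of 8, 8, 8, 8 and 12 weeks.

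**2. Apply the rule to a sequential case.**

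| Row | First visit | Repeat visit | Counted? |
|---|---|---|---|
| ALT or AST >3xULN | yes | no | yes |
| TBL >2xULN | no | yes | yes |
| ALT or AST with TBL | no | no | **no** |
| Hy's Law | no | no | **no** |

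This follows from the text alone. It assumes only that the repeat result is in the trial database.

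**3. Separate the rule from the schedule.** The documents give no episode shapes, so these are assumptions. ALT/AST is above its limit for weeks 0 to a, and TBL for weeks L to L+b. Scheduled draws are S weeks apart with random phase, and t is the time of the first abnormal draw. The same-visit rule is compared with a rule accepting the two limits at any visits. One full-panel repeat may follow r weeks after the first abnormal draw.

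If the episode is no longer than S, at most one scheduled draw falls inside it. On scheduled draws alone both rules then capture the same share: length of overlap / S.

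- Shape (a), a=6, b=6, L=2. Overlap is 6-2 = 4 weeks: 4/12 = 33% (4/16 = 25%) under both rules. With a repeat at 2 weeks, t in 0-6 qualifies under both: 6/12 = 50% (6/16 = 38%).
- Shape (b), a=4, b=4, L=2, repeat at 4 weeks. Same-visit: (4-2)/12 = 17% (2/16 = 13%). Any-visit: t in 0-4, so 4/12 = 33% (4/16 = 25%). Loss from the rule: 2/12 = 17 points (2/16 = 13 points).
- Shape (c), a=3, b=4, L=3, no overlap. Same-visit: 0%. Any-visit with a repeat at 1, 2 or 4 weeks: 1/12, 2/12, 3/12 = 8%, 17%, 25% (1/16, 2/16, 3/16 = 6%, 12-13%, 19%).

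A simulation of 400,000 episodes per setting agrees. A fourth shape (a=8, b=8, L=4) also gave equal capture on scheduled draws at 12 and 16 weeks. At 8-week spacing that 12-week episode can be sampled twice, and same-visit capture was 50% against 100% for an any-visit rule without a time limit.

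**4. Compare a 30-day window with the schedule.** 12 x 7 = 84 days, 16 x 7 = 112 days and 8 x 7 = 56 days all exceed 30. Such a window therefore adds nothing on scheduled draws alone; it works through repeats.

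**5. Unscheduled samples after Week 104.** If the nominal-visit rule shuts repeats out, capture in shape (a) at 12 weeks falls from 50% to 33%, even though those repeats cross both limits together. The SAP does not settle this. Its own example in 17.1 re-aligns a delayed Week 112 visit to Week 116, which is hard to square with nominal visits only after Week 104.

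**6. Up to Week 104.** Visible Group 2 windows run, for example, from Day 394 to 449 (56 days) and from Day 618 to 687 (70 days). If the most-extreme-value rule governs the combined criteria, values from different dates within such a window could count as one visit. The SAP does not say whether it does.

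**The case against.** The strongest reply is that requiring concurrence is clear, pre-specified and specific. ALT, AST, TBL and ALP come from one panel: "Serum chemistries will include glucose, urea, creatinine, total bilirubin, AST (SGOT), ALT (SGPT), GGT, alkaline phosphatase". Every full draw, including a full repeat, can therefore meet the criterion. A wider rule will pair some unrelated values. The analysis is descriptive, and the protocol reports no liver signal in over 6000 exposed patients. All of that stands, and it is why the same-visit count should be kept. It does not answer the case where no single draw crosses both limits.

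A reader might go further and infer three things that the documents do not support.

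- **That the 12-16 week schedule makes the rule lose cases.** Step 3 shows the schedule limiting detection under either rule.
- **That the rule can only lose cases.** Step 6 shows that up to Week 104 it might instead pair values from different dates.
- **That a sequential case would be hidden.** It would not. The single-analyte rows, the listings of all laboratory data and of liver enzyme abnormalities, and the worst-grade CTCAE shift tables would show the separate values. Protocol Appendix 1 also has notable values forwarded to the sponsor, and clinically significant values are adverse events under Protocol 7.1.

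What remains is narrower: none of these outputs is specified to bring the two values together, so the summary row can still read zero.

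**Conclusion.** The point holds as a gap in the summary. A subject with sequential rises is left out of the combined and Hy's Law rows, and after Week 104 the status of unscheduled repeats is undefined. Both follow from the text.

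The size cannot be derived from the documents, which give no duration of either rise, no lag between them and no retest interval. The 0 to 25 points above show only that the loss is nil when the rises overlap at a sampled date and appreciable when they do not. They should not be cited as an expected loss. A cheap improvement to the SAP is warranted; it does not bear on the efficacy results, and the underlying data are still reported.

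**What to change.** Keep the same-visit count and add to SAP 14.2, for example:

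> In addition, a combined criterion is counted when TBL exceeds its limit in the same sample as the qualifying ALT/AST (or ALP) value, or in any scheduled or unscheduled on-treatment sample within 30 days after it. For Hy's Law, the ALP condition is assessed in the qualifying ALT/AST sample. Unscheduled and repeat samples enter Table 14-3 in both core and extension. Values are paired by sample date, not by the most extreme value in an analysis window.

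The 30 days is an example; the team should state its own window before the analysis. Also list, with dates and values, every subject who meets both single-analyte criteria at any time, so that pairs in the other order or outside the window can be seen.

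The cost is a few sentences, one extra row per combined criterion, one listing, and medical review of a few pairs that prove unrelated. No new data are needed, and the same-visit row keeps comparability with other studies. The change does not make up for episodes that fall between scheduled draws.
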